Most studies regarding language acquisition have focused on understanding when and how infants learn words. It is known that at 24 months, typically developing infants know and produce between 200 and 300 words (Jones & Smith, 2005; MacRoy-Higgins, Shafer, Fahey, & Kaden, 2016) and add to their vocabularies from 22 to 37 words each month (Vuksanovic & Bjekic, 2013). It is also during the first years of life that some principles that promote vocabulary learning are developed. The shape bias, which is a tendency to infer that objects that share the same shape will also share the same name, is the one that has been studied the most. At 24 months, typically developed infants present a shape bias and use it as a strategy to generalize words (Jones, 2003; Weismer, Venker, Evans, & Jones Moyle, 2013). In contrast, Late Talkers do not exhibit this preference and present a difficulty in organizing objects by shape (Jones, 2003). It has also been found that teaching typically developed infants a shape bias before the end of the second year of life boosts their vocabulary development (Smith, Jones, Landau, Gershkoff-Stowe, & Samuelson, 2002). Despite this, the possibility of teaching Late Talkers this principle and its effect on their vocabulary and language development has not been explored.

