3.3. Primary outcome measures

Objective A), i.e. whether children have learned a shape bias, will be assessed by means of a noun extension test with novel names and objects never heard and seen before by the infants at the end of the intervention programme.

Objective B), i.e. whether the intervention programme benefits infants' general vocabulary development, will be assessed with a vocabulary checklist filled in by the parents/guardians before and after both types of intervention. We will compare the vocabulary growth in the group of children that took part in the shape bias intervention programme with that of the group of children that took part in the 'specific word' intervention. A significant larger increase in the shape bias intervention compared to the 'specific word' intervention will provide information regarding the success or efficacy of the shape bias intervention.

Objective C), i.e. whether the shape bias intervention has a "long-term" effect on language development and cognitive abilities. Receptive and expressive language, and cognitive abilities, such as visual spatial skills and working memory, will be assessed at one year after the end of the intervention programme.

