4.3.3. Training sessions

4.3.3.1. Shape training: During the first seven weeks, infants will be presented with four novel words paired with four novel sets of objects (total duration 15 minutes). Each set will consist of two exemplars with the same shape but with different colours and textures. Each set will be presented with sentences such as “*Look! It is a kiv. Do you want to play with the kiv?, Let’s play with the kiv*”. Half way through the presentation of the exemplars, the researcher will bring out a third contrasting object. This contrasting object will be presented with the sentence “*Oh no, this is not a kiv*” and will be taken away immediately. The other three sets of novel exemplars will be presented in the same manner.

4.3.3.2. ‘Specific word’ training: This training will resemble a typical word learning intervention. During the first seven weeks infants will be introduced to 28 real common objects and their names (e.g. biscuit, trousers, slide), randomly divided into 7 sets of four words. During each session, infants will be presented with one of the sets and each session will have a total duration of 15 minutes. The target words have been selected from the Wordbank database, an open database that lists the proportion of children that know a specific word at a specific age. Twenty-eight words that 80% of the total child population at 25 months know were randomly selected as target words. Each session will consist of a 15 min play session in which each object name will be presented at least 10 times and each object name will be mentioned at least 10 times. Additionally, techniques such as focused stimulation and modelling target words, which have proved to be useful for word learning, will be used.

4.3.4. First-order generalization: At week 8 infants in both groups will be assessed as to whether they have learned that objects that have the same shape share the same name. They will be presented with each exemplar used during the training sessions accompanied by three novel toys. These three objects will share only one visual property with the training objects (colour, shape or texture). The three objects will be placed on a table and the researcher will say “*This is a kiv, Can you show me the other kiv?*” while he/she shows the infant one of the exemplars used during the 7 training weeks. All infants will be tested on each trained object with the same procedure. This test will last 8 minutes.

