5.5 Risk assessment

Participating in this research study does not represent a greater risk than what infants are exposed to in their everyday environment. The stimuli used are toy-like objects made from paper, clay, and string, the videos are short and age appropriate, and the procedures imitate play sessions. Even though the tasks are child-friendly and interesting, children will be encouraged to continue performing a task if they do not seem motivated. If positive encouragement fails or the child seems uncomfortable or distressed, the researcher will stop the task and/or session, and will give the child his/her reward. The session might be rescheduled if deemed useful and with the approval of the parent/guardian.

The tasks require the child to sit on the parent's/guardian's lab, on a child's chair or on the floor, which will minimize the risk of any falls. The testing area will be child-friendly (eg. electrical sockets covered) and small objects or objects that are not safe for a small child (e.g. scissors, medicines) will be removed from the room prior to the arrival of the participants. Some children might suffer from food allergies, and as in consequence, any food (like biscuits or tea offered to the parents) will be kept in a secure place away from the children. Parents will be present at all times and it will be ensured that all researchers have undergone a DBS check for working with children.

Due to the constant contact between researcher and children, there is a minor risk of contagious diseases such as colds or stomach bugs. In order to minimize the risk, the researcher will wash their hands before and after each session with alcohol based hand wash, and all items that the child might touch, such as toys, chairs and tables, will be cleaned and disinfected after every session. There are no risks to the environment or society arising from this research.

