6.3.1 Summary of baseline data

From the total number of assessments and tasks, results from five of them will be used as baseline data or descriptive statistics. These five assessments are: Vocabulary checklist, Socioeconomic and general development questionnaire, attention task, sorting task, initial working memory assessment, and initial visual spatial abilities assessment. The description of the variables analysed on each assessment and how they will be reported is as follows.

- A. Vocabulary assessment: Parents will fill out this checklist before (and after) the intervention and the total number of words that the infant understands and the total number of words they

produce will be registered as continuous variables and will be considered as the baseline language ability before the intervention programme.

- B. Socioeconomic and general development questionnaire: This questionnaire will provide information regarding general child development, language delay family history, and family status. A number of different types of variables will be collected: nominal variables (e.g. occupation) and ordinal variables (e.g. infant's order of birth). These variables will be used for descriptive statistics. They are potentially interesting as predictor variables, but the sample size is likely too small to draw any strong conclusions.
- C. Attention measure: With this measure, we will assess the fixation duration (number of milliseconds an infant looks) towards a novel object that is moved. The object will be moved for 25 seconds (25000 ms) and the infant's total looking time towards the screen will be registered. This variable will be registered as a continuous variable and used as a predictor of the primary outcome measures.
- D. Sorting task: This will be registered as a categorical variable. Infants will sort objects and depending on their sorting tendency they will be assigned to one of four categories: preference for shape, preference for colour, preference for texture, no preference. This variable will be used as a predictor of the primary outcome measures.

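### Objective B's total-word score counts words taught only to the control arm, so a null or reversed result could not be read as no general-vocabulary benefit

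*Combined protocol and SAP*

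**What the plan says.** Section 3.3 names general vocabulary as the target of Objective B, which "will be assessed with a vocabulary checklist filled in by the parents/guardians before and after both types of intervention". The contrast is between arms, and the criterion for the shape programme is directional: "A significant larger increase in the shape bias intervention compared to the 'specific word' intervention will provide information regarding the success or efficacy".

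The instrument is the UK-CDI Words and Gestures checklist, completed by parents at the first and last of nine weekly sessions (sections 4.2 and 4.3.1). Section 6.3.1 records "the total number of words that the infant understands and the total number of words they" produce. These totals are the only checklist variables that the plan defines.

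The arms are taught different kinds of word. Under section 4.3.3.1 the shape arm meets four novel names, such as kiv. Under section 4.3.3.2 the control arm meets 28 real, common object names, split into seven sets of four with one set per session. On their selection: "Twenty-eight words that 80% of the total child population at 25 months know were randomly selected as target words".

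Section 6.3.2 models vocabulary growth with intervention type and baseline vocabulary among the factors. Nowhere does the plan separate taught from untaught words, or say how many of the 28 are on the checklist.

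**The concern.** The total score mixes two things. One is growth in words that nobody taught in the sessions, which is what a shape bias is meant to promote and what general vocabulary development suggests. The other is direct uptake of target words, which can raise the score in the control arm only: early common nouns are the kind of item a vocabulary checklist holds, and novel names are not.

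Reporting may add to this. Section 5.5 says "Parents will be present at all times", so the control-arm parents who complete the checklist have also watched these words being practised.

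What is at stake is the reading of a result that does not favour shape training. With the total alone, no general benefit cannot be told apart from a general benefit offset by taught words in the comparator.

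**Working it through.** The plan gives no figure for the contribution of taught words, so there is none to reproduce. The 24 completers in section 6.1 enter below only as a sample size. Section 6.1 names neither the test nor a numerical effect size, so 24 cannot be confirmed, and that is a separate matter.

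**1. Scale of the ceiling.** Inputs: 28 target words (section 4.3.3.2); sessions 1 to 9, so 8 weeks between checklists; and the opening background paragraph, where typically developing infants "add to their vocabularies from 22 to 37 words each month".

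- 8 weeks ÷ (52/12) = 1.85 months.
- 1.85 × 22 ≈ 41 words and 1.85 × 37 ≈ 68 words.
- 28/68 = 41% and 28/41 = 69% (68.9% unrounded).

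Section 1.2 describes Late Talkers as having fewer than 50 expressive words at age 2, so 28 is also more than half of that level.

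**2. From ceiling to bias.** Let s be the net share of the 28 words that are on the checklist, unknown at baseline, and gained in the control arm beyond what the shape arm gains on the same words. Then:

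- bias against the shape arm = 28 × s words;
- apparent d = true d − 28s/SD, where true d is the standardised shape advantage on untaught words.

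The documents give neither s nor the SD of growth. Assumed: s = 0.10, 0.25 or 0.50; SD = 20 to 60 words; 12 completers per arm (24 in total, 1:1 allocation assumed); two-sided 5% t-test. The chance of a significant result favouring shape is the probability that a noncentral t on 22 degrees of freedom, with noncentrality d × √(12/2), exceeds the upper 2.5% critical value. With no bias it is 0.22 for d = 0.5 and 0.80 for d = 1.2.

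Each range runs from SD 60 to SD 20:

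| s | 28s (words) | Bias in SD | True d = 0.5 appears as | Chance for d = 0.5 (0.22 unbiased) | Chance for d = 1.2 (0.80 unbiased) |
|---|---|---|---|---|---|
| 0.10 | 2.8 | 0.05 to 0.14 | 0.45 to 0.36 | 0.19 to 0.13 | 0.77 to 0.70 |
| 0.25 | 7 | 0.12 to 0.35 | 0.38 to 0.15 | 0.14 to 0.05 | 0.72 to 0.51 |
| 0.50 | 14 | 0.23 to 0.70 | 0.27 to −0.20 | 0.09 to 0.01 | 0.62 to 0.22 |

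The table illustrates sensitivity and does not estimate the bias. If s is near zero, there is little masking.

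**The case against.** The strongest reply is that this is a choice of question. Section 3.1 words Objective B as a comparison with an intervention that teaches specific words. On that reading, words gained by teaching are the comparator's effect and not contamination, and total words is the natural score. Removing the target words takes out the comparator's direct effect and leaves the shape programme's mechanism almost intact, so shape training could appear to win while adding fewer words overall. This stands. A reader might infer that the total is the wrong score and should be replaced; the documents do not support that, and the total should stay as the head-to-head comparison.

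The second reply concerns size, and it also stands. Each set of four words gets one 15-minute play session, with at least 10 mentions of each name. Participants are 24 to 48 months old (section 4.1.1), and the words are ones that most children know at 25 months. Some will be known at baseline, particularly among words understood, and some will be learned in the shape arm too. A reader might infer that the control arm gains 28 words, or that 10 to 28 learned words would cancel a medium effect. The first treats a ceiling as an estimate. The second is only half of an assumed SD of 20 to 56 words, and the documents give no SD.

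Third, the bias is conservative for the stated success criterion, and a null at about 12 per arm is weak evidence anyway (0.22 for d = 0.5 with no masking). This stands in part. Low power widens the uncertainty, whereas taught words shift the contrast in one direction, and a larger sample would not remove the shift.

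Finally, the week 9 test uses wholly new objects (section 4.3.5) and the model includes baseline vocabulary (section 6.3.2). Neither separates taught from untaught words in the checklist score.

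**Conclusion.** The point holds as a limit on interpretation. The plan states a general-vocabulary aim, scores it with totals that can include words taught in one arm only, and offers no way to separate the two. A null or reversed total-word contrast therefore could not support a conclusion of no general benefit. A significant shape advantage would stand despite the bias.

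The size is not determined by the documents. It depends on checklist overlap, baseline knowledge, uptake in each arm and the SD of growth, none of which is given. The ceiling's 41% to 69% share is measured against growth in typically developing infants, not in this population. The net gain is probably well below the ceiling, but under the assumed SDs a net 7 words would still move the contrast by 0.12 to 0.35 SD.

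**What to change.** In section 6.3.2:

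- Keep total words as the head-to-head comparison with word teaching.
- State how many of the 28 target words are on the UK-CDI.
- Pre-specify one companion between-arm analysis of growth with those words removed, in both arms and at both time points. Use the same model and the same score (understood or produced) as the total-word comparison.
- Base any statement about general (untaught) vocabulary on that companion analysis.
- Report the 28-word subscore by arm, descriptively only.

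No new data collection is needed, because the forms are already planned. Section 6.3.1 mentions only totals, so the responses to the overlapping items must be entered individually: at most 28 × 2 = 56 entries per child for each score.

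The downside is one more analysis on a slightly shorter scale. Label it supportive, so that it does not become a competing primary test in a sample of about 24.

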4.4. Procedure of follow up study

A follow up study will be conducted one year after the start of the intervention programme in order to assess the long-term effects of the intervention in language and cognitive development. For this follow up study children's language, and cognitive abilities, will be assessed. The British Picture Vocabulary Scale (BPVS3) will be used to assess receptive language. In this test the child will listen to a word and will have to select from a set of pictures, the image that corresponds to that word. The Wechsler Preschool & Primary Scale of Intelligence - Fourth UK Edition (WPPSI-IV UK) will be used to assess infant's visual spatial skills and working memory. In this test, the child will be asked to recreate different figures using blocks and to view animal cards on a zoo layout for a specified time, remember where they are located, and then place each card in the previously viewed location.

5. Ethical considerations

5.1 Research Ethics Committee review and reports

Before the start of the recruitment process, approval will be sought from the ethics committee of the University of Birmingham in addition to an NHS Research Ethics Committee. Additionally, each year an annual progress report will be submitted by the Chief Investigator to the NHS Research Ethics Committee until study completion. When the study is concluded, the Chief Investigator will notify the Research Ethics Committee and one year after this, the chief Investigator will submit a final report with the results of the study.

5.2 Peer review

A research proposal of the present study was reviewed by a colleague of the Chief investigator at the School of Psychology at the University of Birmingham as part of the main researcher's progress review of her PhD project. The project was discussed in a formal viva voce in which feedback regarding the research questions, methodology and design was provided. The reviewer is not involved in the study in any way, but was chosen because of his expertise in the field of developmental psychology, which includes developmental experimental design and the recruitment and testing of child participants.

5.3 Public and Patient Involvement

The study was presented to the NIHR Clinical Research Network: West Midlands – Young Person's Steering Group (YPSG) in a meeting held at the University of Birmingham. In this meeting, the Chief Investigator and Main Researcher explained the study, its main objectives, methodology and importance for the field. Additionally, the Chief Investigator and Main Researcher presented the recruitment flyer, the information sheet for parents and the consent form. The members of the Young Person's Steering Group provided feedback on how to improve these documents in terms of readability and informativeness. Furthermore, they also provided ideas on how to explain the tasks to the infants in a child friendly language. At the end of the study there will be a second meeting with this group to report on the study's findings.

5.4 Indemnity and Participants payment

Parents will be offered reimbursement for travel expenses for every session that they attend at the Infant and Child Laboratory. Infants will receive a sticker every session they attend and will also receive a book or toy worth not more than £5 after attending all nine sessions.

5.5 Risk assessment

Participating in this research study does not represent a greater risk than what infants are exposed to in their everyday environment. The stimuli used are toy-like objects made from paper, clay, and string, the videos are short and age appropriate, and the procedures imitate play sessions. Even though the tasks are child-friendly and interesting, children will be encouraged to continue performing a task if they do not seem motivated. If positive encouragement fails or the child seems uncomfortable or distressed, the researcher will stop the task and/or session, and will give the child his/her reward. The session might be rescheduled if deemed useful and with the approval of the parent/guardian.

The tasks require the child to sit on the parent's/guardian's lab, on a child's chair or on the floor, which will minimize the risk of any falls. The testing area will be child-friendly (eg. electrical sockets covered) and small objects or objects that are not safe for a small child (e.g. scissors, medicines) will be removed from the room prior to the arrival of the participants. Some children might suffer from food allergies, and as in consequence, any food (like biscuits or tea offered to the parents) will be kept in a secure place away from the children. Parents will be present at all times and it will be ensured that all researchers have undergone a DBS check for working with children.

Due to the constant contact between researcher and children, there is a minor risk of contagious diseases such as colds or stomach bugs. In order to minimize the risk, the researcher will wash their hands before and after each session with alcohol based hand wash, and all items that the child might touch, such as toys, chairs and tables, will be cleaned and disinfected after every session. There are no risks to the environment or society arising from this research.

Parents/guardians will be informed at session 1 that if during any of the sessions the child or parent/guardian discloses information that might lead the researcher to think that the child or anyone else is at risk, or is being abused, then this information will have to be disclosed to the research team and the relevant authorities. If it is something serious that occurs during the testing session, the assessments will be stopped and the Chief Investigator will be informed immediately. In both cases, the government advice on the procedures for these events will be followed (as outlined at <https://www.education.gov.uk/publications/standard/publicationDetail/Page1/DFES-04319-2006>).

5.6 Data protection and confidentiality

All researchers involved in the study will comply with the requirements of the Data Protection Act 1998 regarding collection, storage, processing and disclosure of personal information and will uphold the Act's core principles which state that all data must be:

- A. Fairly and lawfully processed
- B. Processed for specified purposes
- C. Adequate, relevant and not excessive
- D. Accurate
- E. Not kept longer than necessary
- F. Processed in accordance with the subject's data rights
- G. Secure from unauthorised access or alteration
- H. Not transferred to countries without adequate data protection

In order to maintain confidentiality, each participant will receive a participant code formed by an unrelated sequence of characters. During the collection and analysis of data, any data related to the participant will be identified by this code. The documents/hard copies containing the linking code with the personal information will be stored separately from all data in a locked cabinet (when used hard copies) or in a password protected computer and in a password protected/encrypted file (when stored electronically).

The Chief investigator will act as the data custodian. If data is shared with the sponsor or research team, it will not contain information that could lead to the identification of a specific participant. However, personal data will need to be shared with the researcher who conducts the follow-up study in order to contact the parents/guardians. But any newly collected data will again be marked by the participant ID.

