3.1. Primary objectives

The main objectives of the present study are:

- A. To investigate whether it is possible to teach Late Talkers to attend to objects' shapes as a useful property for learning and generalizing novel object labels.
- B. To assess the benefits that this intervention programme has on Late Talkers' short-term vocabulary development compared to an intervention where infants will be taught specific words ('specific word' intervention).
- C. To assess the benefits of the intervention programme on language and cognitive development one year after the intervention compared to the 'specific word' intervention.

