4.2. Study design

Infants will be randomly allocated to one of two groups: shape training group or specific word training group. Over a series of 9 weekly sessions, all infants will be assessed on different tasks that can be divided into 5 stages: Vocabulary and developmental assessments, initial cognitive assessments, training sessions, first-order generalization test, higher-order generalization test. Depending on the group that the children will be in, they will receive either a shape training or a specific word training. Other assessments (initial assessments, cognitive assessments, first-order generalization test and higher-order generalization test) will be identical across the groups. Additionally, a follow up study will be conducted after one year of completion of the intervention programme. A table describing the intervention procedure is provided in Figure 1. Details of the tasks are given below.

[figure not shown]

Figure 1. Timeline of intervention programmes.

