4.3.5. Higher-order generalization: At week 9, all infants will be assessed with four pairs of novel objects different to the ones used in previous sessions. The same procedure as the one for the first-order generalization will be followed and it will also last 8 minutes. This test will assess if infants have learned a general rule that one can extend novel labels based on shape similarities.

At the end of the study and independent of the type of intervention that the children took part in, parents/guardians will be asked about their thoughts about the development and implementation of the study, as well as about possible changes they made at home or any activities (such as music or dancing sessions) that their infants attended to while they were part of the study (see Appendix 1.6). Additionally, they will receive a Participant Debrief Sheet with more information about the specific intervention programme that their child received (see Appendix 1.7).

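### Nothing in the plan keeps the allocation from the person who gives the one-year tests, although Objective C is a primary comparison between the two interventions

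*Combined protocol and SAP*

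**What the plan says.** Allocation is random (section 4.2): "Infants will be randomly allocated to one of two groups: shape training group or specific word training group". No section mentions blinding, masking or allocation concealment.

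Objective C, listed among the primary objectives in 3.1, concerns "language and cognitive development one year after the intervention compared to the 'specific word' intervention". Section 3.3 places the one-year language and cognitive measures among the primary outcomes.

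Section 4.4 names the instruments. "The British Picture Vocabulary Scale (BPVS3) will be used to assess receptive language", by having the child choose a picture for a spoken word. The WPPSI-IV covers visual spatial skills and working memory through block and card tasks.

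On who does the testing, section 5.6 says that "personal data will need to be shared with the researcher who conducts the follow-up study", the purpose being to contact families, and that "any newly collected data will again be marked by the participant ID". It does not say whether the group may be passed on with the contact details.

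On what parents know, section 4.3.5 says that at the end of the programme "they will receive a Participant Debrief Sheet with more information about the specific intervention programme that their child received".

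**The concern.** A face-to-face tester who knows the child's group can, without meaning to, encourage, pace or score differently in the two arms. Section 5.5 expects researchers to encourage children who lose motivation, so there is room for this. If it happens, the bias enters the recorded scores, and no later analysis can separate it from a treatment effect.

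The plan already has most of what masking needs: an apparently different tester, a deliberate hand-over of limited information, and coded participant IDs. It lacks the instruction that would use them. This is therefore a procedure that could be improved, and more than a missing description.

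**Working it through.** The point is textual, so the sections are set side by side first. A labelled illustration follows.

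**1. Is the one-year outcome a primary between-arm question?** Yes, by 3.1 and 3.3.

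**2. Is the tester a different person?** Section 5.6 says personal data must be handed over so that this researcher can contact families. That would be unnecessary if the tester already held the details. A different person is the natural reading, but it is an inference: 4.1.5 calls the person who contacts families about follow-up simply the researcher, the term also used for whoever runs the sessions in 4.3.

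**3. Does any section withhold the allocation from that person?**
- 5.6 limits the sharing to a purpose (contacting families) and lists data-protection principles, including that data should not be excessive. Participant codes protect identity; they are not described as hiding the group.
- 7.2 restricts questionnaires, assessments and case report forms to two roles.
- 7.4 gives the research team the complete dataset.
- The parent's blacked-out glasses in 4.3.2 belong to the baseline eye-tracking task and have nothing to do with allocation.

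The first two are confidentiality rules, and 7.4 points the other way. None settles whether the follow-up tester may know the group.

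**4. Can the group become known by another route?** Yes. The debrief in 4.3.5 comes before follow-up, and 5.5 has parents present throughout.

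**5. Which analysis would be affected?** Objective C promises a comparison between arms. Section 6.3.2 describes only a comparison of follow-up scores with the standardised UK mean, and specifies no between-arm follow-up test. Hiding the arm protects the first. It does little for the second, because the tester would still know that every child had been in a programme.

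**6. Illustration only, for an assumed test.** The plan has no figure to reproduce here. Assume a two-sample t-test between arms, two-sided 5%, equal arms, no true effect, and a tester-induced shift of b SD between arms. None of these assumptions comes from the documents. The arm sizes are half of the 24 completers and half of the 30 recruits in 6.1, so 24/2 = 12 and 30/2 = 15. The rejection rate is the probability that a noncentral t with 2n − 2 degrees of freedom and noncentrality b√(n/2) exceeds the critical value in absolute size.

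| n per arm | df | critical t | b (SD) | b√(n/2) | rejection rate |
|---|---|---|---|---|---|
| 12 | 22 | 2.074 | 0.1 | 0.245 | 5.6% |
| 12 | 22 | 2.074 | 0.2 | 0.490 | 7.6% |
| 12 | 22 | 2.074 | 0.3 | 0.735 | 10.8% |
| 15 | 28 | 2.048 | 0.1 | 0.274 | 5.8% |
| 15 | 28 | 2.048 | 0.2 | 0.548 | 8.3% |
| 15 | 28 | 2.048 | 0.3 | 0.822 | 12.5% |

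Follow-up numbers could be lower than this, because families consent to follow-up contact separately (4.1.4) and may decline it (4.1.5). The table shows only that a small shift would be nearly invisible and a larger one would not. It does not estimate the bias in this trial.

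**The case against.** The strongest reply is that the plan contains no between-arm follow-up test, so there is no planned contrast for an unmasked tester to distort. This stands as a limit on the point: the benefit is to the comparison in Objective C, which 6.3.2 does not carry through. It does not remove the point, because that comparison is a stated primary objective and would have to use these scores.

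A second reply is that picture choice, block copying and card placement on standardised tests leave the score largely to the child. This is fair and keeps the likely effect small, but encouragement and prompting remain in the tester's hands.

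A third is that 5.6 and 7.2 already limit what the tester receives. They do so for confidentiality, and 7.4 leaves the matter open.

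Several stronger readings are tempting and are not supported:
- That this is the only primary outcome that could be masked. The noun extension test for Objective A is also run by a researcher, with the same procedure in both arms (4.3.4, 4.3.5). It could be masked with a second examiner or masked scoring, though the plan names no such person. Only the parent checklist for Objective B has no examiner to mask.
- That masking costs nothing or removes the bias. It needs some administration, and debriefed parents may disclose.
- That a separate tester is stated. It is inferred.
- That the bias can be sized against a 0.5 SD effect in 6.1. That section says only that the effect is medium, with no metric or test.

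**Conclusion.** The point holds in this limited form: no section keeps the allocation from whoever gives the one-year BPVS3 and WPPSI-IV tests, and the plan already appears to have a person who could be masked with little effort. Tester expectation is therefore an uncontrolled source of bias in the between-arm contrast of a primary objective.

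Its size is unknown. The documents give nothing to estimate it from, and the rejection rates above depend wholly on an assumed shift and an assumed test. The conclusion rests on two readings: that the hand-over in 5.6 implies a different tester, and that the Objective C comparison will in fact be made. If the tester also delivered training, withholding a list would mask nothing, and the plan would need to say so. This should be changed before follow-up testing begins.

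**What to change.** In 4.4 and 5.6, state that:
- the follow-up tester is someone who did not deliver the training, as 5.6 implies;
- this person receives contact details and participant ID only, and is given neither the allocation nor any intervention-phase data until follow-up scores have been entered;
- parents are asked, when the visit is booked, not to say which programme the child had;
- any unmasking is recorded, with when and how it happened, and reported.

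Add to 7.4 that the research team's access to the complete dataset does not extend to the follow-up tester before that point.

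The cost is protocol wording, a booking script, custody of the allocation list and a short log. If the tester is a different person, as 5.6 suggests, no extra staff are needed; if not, one would have to be found. No instrument, visit or sample size changes. Separately, 6.3.2 should specify the between-arm follow-up comparison that Objective C promises, since that is the analysis that masking protects.
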